2.3.8.5. Exploratory Analyses

To explore the potential benefit, efficacy signal of imetelstat on MF patients, exploratory analyses may be conducted include but not limited to:

- TSS score, spleen volume and spleen length will be summarized over time, along with plots.
- Waterfall plots of TSS score, spleen volume, and spleen length collected at Week 24 will be generated to evaluate pattern of changes from baseline.
- Time to spleen response, which is defined as time from date of the Cycle 1, Day 1 to the date of the first documented spleen response (SVR \geq 35%), will be descriptively summarized for subjects who achieve spleen response.
- Time to symptom response, which is defined as time from date of the cycle 1, Day 1 to the date of the first documented symptom response (TSS \geq 50%), will be descriptively summarized for subjects who achieve symptom response.
- Time to anemia response will be descriptively summarized for anemia responders per modified IWG-MRT criteria.
- Improvement of fibrosis grade is defined as a fibrosis grade better than baseline fibrosis grade. The proportion of subjects who achieve improvement of fibrosis grade for the treated population will be summarized.

For interim analysis, Week 12 data will be used instead of Week 24 when it is applicable, including, but not limited to, leukemia free survival, bone marrow (fibrosis grade, blasts, cellularity), transfusion reduction/ transfusion independence.

To explore the potential benefit related to transfusion, the analyses of rate of 12-week RBC TI response and time to 12-week RBC TI response will be performed.

2.3.8.6. Patient-Reported Outcomes (PRO)

2.3.8.6.1. EORTC QLQ-C30

EORTC QLQ-C30 includes 30 separate items resulting in 6 functional scales (global health status, physical functioning, role functioning, emotional functioning, cognitive functioning, and social functioning) plus 3 symptom scales (fatigue, nausea and vomiting, and pain), Scores will be derived using validated scoring algorithms according to EORTC QLQ-C30 Scoring Manual (3rd Edition, 2001).

2.3.8.6.2. EQ-5D-5L

The EQ-5D is a 5-item questionnaire and a “thermometer” visual analogue scale ranging from 0 (worst imaginable health state) to 100 (best imaginable health state). The scores for the 5 separate questions are categorical and should not be analyzed as ordinal numbers.

The scores for the 5 categorical dimensions will be used to compute a single utility score ranging from zero (0.0) to 1 (1.0) representing the general health status of the individual. The United Kingdom weights will be used to generate patient utilities from the 5 dimensions of the EQ-5D in this study.

2.3.8.6.3. Brief Pain Inventory (BPI)

The BPI is a 7-item questionnaire.

2.3.8.6.4. Patient's Global Impression of Change (PGIC)

The PGIC is a questionnaire form with scores ranging from 1 (Very much improved) to 7 (Very much worse).

2.3.8.6.5. Analysis Methods for PRO

Descriptive statistics (N, mean, SD, median, minimum, maximum) at baseline and each post-baseline time point is reported by treatment arm for each scale of EORTC QLQ-C30, EQ 5D visual analogue scale and weighted utility score, BPI, and PGIC. Analyses of compliance will be performed for each PRO measures.

The PRO measure of interest is EORTC-QL-C30 and BPI. Value of threshold for improvement/worsening is estimated by distribution based method. Specifically, improvement/ worsening is defined as \geq half of standard deviation at baseline points for each assessment post baseline (add ref Norman 2003). Rate of improvement/worsening, and time to improvement/worsening for EORTC-QL-C30 and BPI will be summarized for each treatment arm.

2.3.8.7. Biomarker

Biomarker parameters of Telomerase Activity (TA), Telomere Length (TL), hTERT RNA Expression (hTERT), molecular response and Cytogenetic response will be assessed at day 1, day 8 of Cycle 1, day 1 of cycle 2, at time of CR/PR, and at time of PD. The change and percent change of each parameter (TA, TL, and hTERT) will be summarized (N, mean, SD, minimum, maximum) at each scheduled assessment visit, along with plots. Cytogenetic response rate and molecular response will be derived according to IWG-MRT criteria and will be summarized based on biomarker evaluable population. A separate biomarker SAP may be prepared, and results of biomarker analyses may be presented in a separate report.

2.3.9. Safety

The safety of the treatment arms will be summarized using laboratory test results, vital sign measurements, physical examination results, and the incidence and severity of adverse events.

2.3.9.1. Adverse Events

Treatment-emergent adverse events are defined as any adverse event that occurs after administration of the first dose of study drug and through 30 days after the last dose of study drug, any event that is considered drug-related (possibly, probably, or possibly related) regardless of the start date of the event, or any event that is present at baseline but worsens in intensity or is subsequently considered drug-related by the investigator. The severity of adverse events will be assessed using NCI CTCAE Version 4.0.

The Medical Dictionary for Regulatory Activities (MedDRA version 20.0) dictionary will be used to code the investigator's adverse event terms to preferred term and system organ class. Adverse event tables will summarize incidence by the treatment arm actually received.

For each AE, its relationship to study drug is determined by the investigator and recorded on the CRF. An adverse event is considered as related to study drug if it is possibly, probably, or very likely related to study drug imetelstat.

An overview of treatment-emergent adverse events as well as the incidence of treatment-emergent adverse event will be summarized. The following tabulations will also be presented:

- Incidence of treatment-emergent adverse events by system organ class and preferred term.
- Incidence of treatment-emergent adverse events, especially the most commonly reported events, ie, those events reported by at least 5% of subjects, by MedDRA system organ class and preferred term.
- Incidence of treatment-emergent adverse events considered by the investigator to be related to study drug, by system organ class and preferred term.
- Incidence of treatment-emergent adverse events by CTCAE toxicity grade.
- Incidence of treatment-emergent adverse events leading to withdrawal from treatment by system organ class and preferred term (adverse events leading to discontinuation of all study drugs).
- Incidence of treatment-emergent adverse events leading to death by system organ class and preferred term.

For treatment-emergent adverse events with CTCAE toxicity Grade 3, 4, or 5, the following summaries are to be produced:

- Incidence of Grade 3, 4, or 5 treatment-emergent adverse events, by system organ class and preferred term.
- Incidence of Grade 3, 4, or 5 treatment-emergent adverse events considered by the investigator to be related to study drug, by system organ class and preferred term.

For treatment-emergent serious adverse events, the following summaries are to be produced:

- Incidence of treatment-emergent serious adverse events, by system organ class and preferred term.
- Incidence of treatment-emergent serious adverse events considered by the investigator to be related to study drug, by system organ class and preferred term.
- Incidence of treatment-emergent serious adverse events by relationship to study drug.

The subgroup analyses of adverse events will be done as specified in [Section 2.1.3.5](#).

Tabulation for adverse events of interest (hepatic AE, site reaction AE) will be provided. Details will be specified in Data Presentation Specifications (DPS).

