- Beginning with Protocol Amendment 2, subjects in Arm B (4.7 mg/kg) may continue to receive their current imetelstat dose or have the dose increased to 9.4 mg/kg at the investigator's discretion and according to the guidance provided in Section 6. Dose escalation for these subjects may occur at any cycle of the Treatment Phase. Subjects who have their dose increased will have additional MRI and spleen assessments before receiving the first dose of imetelstat 9.4 mg/kg. Additional blood samples will be collected for biomarker assessments before and after the first dose of imetelstat 9.4 mg/kg, and blood samples for PK assessment will be collected after receiving the first dose of imetelstat 9.4 mg/kg.

TIME AND EVENTS SCHEDULE (EXTENSION PHASE)

Use this Time and Events Schedule after local IEC/IRB approval of Amendment 3.

Study Procedures	All Subjects	Extended Treatment (21-day treatment cycle)	Extended Follow-up (Every 16 weeks ± 7 days)
Informed consent	Xa		
Dispense/administer study drug		X (Day 1)	
Serious adverse event monitoring ^b		X^{b}	
Survival status			X ^c

a All subjects must provide informed consent to enter the Extension Phase. This must occur before the first dose of imetelstat for subjects continuing treatment in the Extension Phase.

Submit a Serious Adverse Event Form to the sponsor within 24 hours of awareness of the event for all serious adverse events. If the subject has a hemorrhagic serious adverse event, INR (or PT), aPTT, and platelet count will be assessed and reported in the serious adverse event report. If the subject experiences a hepatic serious adverse event, serum chemistry and an expanded liver panel will be assessed and reported; if the event includes Grade 3 or 4 ALP elevation, ALP fractionation or 5'neucleotidase will also be assessed and reported. Serious adverse events will be reported from the time the Extension Phase ICF is signed and dated until 30 days after the last dose of imetelstat.

c Assessment of survival status is required for all subjects who enter the Extension Phase, including those who discontinued treatment during the main study.

TIME AND EVENTS SCHEDULE (PK SAMPLING)

Study Day	PK Blood Sampling Time ^a	Serial (Intense) PK Blood Sampling ^b	Sparse PK Blood Sampling ^b	Sparse PK Blood Sampling Dose Escalation (4.7 to 9.4 mg/kg) ^e
Cycle 1, Day 1	0 (before start of infusion)	X		
Cycle 1, Day 1	1 h	X		
Cycle 1, Day 1	2 h ^c	X		
Cycle 1, Day 1	3h-5h	X		
Cycle 1, Day 1	6h-10h	X		

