3.2.1. Rationale for Protocol Changes Following the First Interim Review

The first interim data review to assess safety and early efficacy, and to perform comprehensive exposure-response analyses was performed after approximately 20 subjects in each arm were followed-up for at least 12 weeks. The safety analysis for this interim review included data for 79 subjects (40 in the 4.7 mg/kg arm; 39 in the 9.4 mg/kg arm) who received at least 1 dose of study drug. The efficacy analysis included 40 evaluable subjects (20 in 4.7 mg/kg arm; 20 in the 9.4 mg/kg arm) who received at least 1 dose of study drug, had a baseline MRI, and at least 1 post-baseline MRI assessed by investigator.

First Interim Review of Safety

The patient populations enrolled into each arm were balanced in terms of type of myelofibrosis (primary-MF, PPV-MF, or PET-MF) and DIPSS prognostic risk.

With a median treatment duration of 4 cycles (range 1-15 cycles), both the 4.7 mg/kg and
9.4 mg/kg arms were found to have an acceptable safety profile consistent with that observed in
prior studies with imetelstat.

First Interim Review of Efficacy
The landmark analysis of spleen response demonstrated that at Week 12,
• • • •
First Interim Review of PK
First Interim Review of PK No prior PK data were available from subjects with myelofibrosis.
No prior PK data were available from subjects with myelofibrosis.
No prior PK data were available from subjects with myelofibrosis. Summary
No prior PK data were available from subjects with myelofibrosis.
No prior PK data were available from subjects with myelofibrosis. Summary

Consequently, the following protocol changes will be implemented with Protocol Amendment 2:

- Enrollment of new subjects was suspended for Arm A (9.4 mg/kg) and permanently closed for Arm B (4.7 mg/kg).
- Subjects currently in the 9.4 mg/kg arm may continue treatment at the investigator's discretion.
- Subjects in the 4.7 mg/kg arm may continue to receive treatment and may have their dose escalated to 9.4 mg/kg if pre-defined safety parameters are met and at the investigator's discretion (see Section 6). Subjects who have clinical benefit per investigator assessment but do not meet eligibility for dose escalation may choose to continue to be treated with the 4.7 mg/kg dose and continue assessments per protocol.

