11.9. Safety Analyses

Safety analyses will be performed using the Treated Population. Safety will be evaluated using the NCI-CTCAE (Version 4.03). The safety parameters to be evaluated are the incidence, intensity, and type of adverse events, clinically significant changes in the subject's physical examination findings, vital signs measurements, clinical laboratory results (hematology and chemistry), and deaths. Exposure to study treatment and reasons for discontinuation will be tabulated. Safety

variables are to be tabulated by descriptive statistics (n, mean, median, SD, minimum, and maximum; or n and percent).

Additional analyses will be performed for the subjects who were initially treated with imetelstat 4.7 mg/kg and subsequently dose escalated to 9.4 mg/kg per the guidance outlined in Section 6.

Adverse Events

Treatment-emergent adverse events are adverse events that occur after the first dose of study drug, through the Treatment Phase, and for 30 days following the last dose of study drug; any adverse event considered study drug-related regardless of the start date of the event; or any event that is present at baseline but worsens in severity or is subsequently considered drug-related by the investigator. The number and percent of subjects with treatment-emergent adverse events will be summarized according to intensity (NCI-CTCAE, Version 4.03) and drug relationship as well as categorized by System Organ Class and preferred term by treatment arm.

The verbatim terms used in the CRF by investigators to identify adverse events will be coded using the Medical Dictionary for Regulatory Activities (MedDRA). Treatment-emergent adverse events are adverse events with onset during the treatment phase or that are a consequence of a pre-existing condition that has worsened since baseline. All reported adverse events will be included in the analysis. For each adverse event, the percentage of subjects who experience at least 1 occurrence of the given event will be summarized by treatment arm.

Clinical Laboratory Tests

Laboratory data will be summarized by type of laboratory test. Reference ranges and markedly abnormal results (specified in the Statistical Analysis Plan) will be used in the summary of laboratory data. Descriptive statistics will be calculated for each laboratory analyte at baseline and for observed values and changes from baseline at each scheduled time point.

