The first interim review planned in this study occurred after the first 40 evaluable subjects (defined as the subjects who have both baseline and post baseline spleen measurement per investigator MRI, 20 per treatment arm) were followed for at least 12 weeks. Both arms would continue with enrollment until approximately 100 subjects per arm were enrolled if both of them were efficacious and had an acceptable safety profile. If only one arm was efficacious and had an acceptable safety profile, then that arm would continue enrollment and enrollment would be stopped in the other arm. In the case that both arms were not efficacious and safe, an alternative dose may be selected based on the PK/PD exposure-response, efficacy, and safety analysis and a protocol amendment would be implemented to reflect this.

Following the first interim review of data, and in line with Protocol Amendment 2, enrollment of new subjects into Arm A was suspended and enrollment into Arm B was permanently closed. Subjects in Arm B continued their current treatment or had their dose increased to 9.4 mg/kg at the investigator's discretion according to the guidance provided in Section 6 of protocol. Subjects in Arm A could have continued treatment at the investigator's discretion.

The second interim review was performed with a clinical cutoff that was 6 months after the clinical cutoff used for the first interim review. Following the second interim review, it was decided that enrollment in Arm A would be permanently closed.

The analyses specified in the SAP are considered the final analyses for the protocol, with a data cut-off of 18 months after the last subject was enrolled. Data collected in the extension phase will not be included in the analyses and will not be reported here. There will be a separate addendum with data from that phase.

The final decision for further development will be made based on the totality of data taking into consideration efficacy data, including spleen responses, symptoms, peripheral blood counts, bone marrow data, survival, safety, and PK/PD data.

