2.1.3. Data Handling Rule and Imputation of Missing Data

In general, no missing data, other than missing dates specified below, will be imputed. For subjects who had dose escalation (from 4.7 mg/kg to 9.4 mg/kg), data up to dose escalation will be included in tables generated for CSR. Data after dose escalation (inclusive) will be listed only.

Imputation of partial missing dates will be made for AE onset date, AE resolution date, date of death, start and end dates of concomitant therapy, and date of initial diagnosis.

For AE onset and resolution date, the global standard AE imputation rules listed below will be applied.

Partial AE onset dates will be imputed as follows:

- If the onset date of an adverse event is missing day only, it will be set to:

- First day of the month that the AE occurred, if month/year of the onset of AE is different than the month/year of the first dose date
- The day of first dose date, if the month/year of the onset of AE is the same as month/year of the first dose date and month/year of the AE resolution date is different
- The day of first dose date or day of AE resolution date, whichever is earliest, if month/year of the onset of AE and month/year of the first dose date and month/year of the AE resolution date are same
- If the onset date of an adverse event is missing both day and month, it will be set to the earliest of:
 - January 1 of the year of onset, as long as this date is after the first dose date
 - Month and day of the first dose date, if this date is the same year that the AE occurred
 - The AE resolution date.
- Completely missing onset dates will not be imputed.
- Partial AE resolution dates not marked as ongoing will be imputed as follows:
 - If the resolution date of an adverse event is missing day only, it will be set to the earliest of the last day of the month of occurrence of resolution or the day of the date of death, if the death occurred in that month.
 - If the resolution date of an adverse event is missing both day and month, it will be set to the earliest of December 31 of the year or the day and month of the date of death, if the death occurred in that year.
 - Completely missing resolution dates will not be imputed.

For start and end dates of concomitant therapies, the global standard AE imputation rules listed above will be applied accordingly.

For date of death and date of initial diagnosis, the following rule will be applied.

- If date is completely missing, no imputation will be made.

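### Adverse-event percentages by arm mix toxicity with unequal observation time, because Arm B data stop at escalation and Arm A data do not

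*SAP*

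**What the plan says.** - **Measure.** SAP 2.3.9.1: "Adverse event tables will summarize incidence by the treatment arm actually received". Every adverse-event tabulation listed there is an incidence. Protocol 11.9 defines the measure: "the percentage of subjects who experience at least 1 occurrence of the given event will be summarized by treatment arm". Neither section gives a rate per unit of time, a common-window table or a time-to-first-event summary for adverse events.
- **Arm B.** SAP 2.1.3, on subjects who escalate: "data up to dose escalation will be included in tables generated for CSR. Data after dose escalation (inclusive) will be listed only".
- **Arm A.** SAP 1.2 records that after Amendment 2 "Subjects in Arm A could have continued treatment at the" investigator's discretion. No cut applies, and the treatment-emergent window runs "through 30 days after the last dose of study drug".
- **Timing and selection.** Footnote w of the Time and Events Schedule (Main Study): "Dose escalation for these subjects may occur at any cycle of the Treatment Phase". Protocol Section 6 limits escalation to subjects whose hematology and biochemistry values meet the entry limits, who meet no dose-modification threshold, and who have never had a dose reduction.
- **Related outputs.** SAP 2.3.6 summarizes cycles and duration of exposure separately. SAP 2.3.9.2 gives mortality 30 and 60 days after first dose. SAP 2.3.9.3 gives shift tables by cycle for selected laboratory parameters.

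**The concern.** A crude percentage of subjects with at least one event rises with time observed. Here that time is shortened by rule for one group only: Arm B subjects who escalate. The shortening is also selective, since these subjects were still on drug and tolerating it, so the later follow-up lost to the tables is theirs.

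The study's primary objective covers two dose regimens, and SAP 1.2 bases further development on the totality of data, including safety. Adverse-event percentages in adjacent columns will naturally be read across. A reader could then take a difference in follow-up for a difference in tolerability.

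**Working it through.** The documents state no adverse-event rate, number escalated, escalation time or exposure by arm, so there is no plan figure to reproduce. Protocol 3.2.1 gives a median of 4 cycles (range 1 to 15) at the first interim review, without a split by arm; that does not date the escalations. What follows is an illustration on assumed inputs.

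**Inputs (all assumed).** Event risk per cycle q = 5%, the same in both arms. Discontinuation per cycle d = 8%, unrelated to events. Cap K = 23 cycles. A share f = 30% or 50% of Arm B is assigned a cut after Cycle 5, whether or not still on treatment then. The 30-day tail is ignored. As a rough check on K, the SAP cutoff is 18 months after last enrolment: 18 × 30.4375 / 21 = 26 cycles.

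**Formula.** With r = (1−q)(1−d), crude incidence over K cycles is I(K) = q(1−r^K)/(1−r).
- r = 0.95 × 0.92 = 0.874.
- Arm A: I(23) = 0.05 × (1−0.0452)/0.126 = 37.9%.
- Cut after Cycle 5: I(5) = 0.05 × (1−0.5100)/0.126 = 19.4%.
- Arm B: f·I(5) + (1−f)·I(23) = 32.4% (f = 30%) or 28.7% (f = 50%).

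**Sensitivity.**

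| Change | Arm A | Arm B, f = 30% | Arm B, f = 50% |
|---|---|---|---|
| Base case | 37.9% | 32.4% | 28.7% |
| q = 10% | 57.4% | 50.8% | 46.4% |
| Front-loaded risk: 10% in Cycles 1–2, then 1% | 24.9% | 23.5% | 22.5% |
| Arm A discontinuation 12% per cycle, Arm B 8% | 30.0% | 32.4% | 28.7% |

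- **Cap.** At q = 5%, caps from 18 to 60 cycles give a gap of 5.0 to 6.1 points (f = 30%) or 8.4 to 10.1 points (f = 50%).
- **Meaning of f.** Only 0.92^5 = 65.9% remain on treatment after Cycle 5, so f = 30% or 50% means that 19.8% or 33.0% of Arm B actually escalate. If 30% or 50% actually did, f becomes 0.30/0.659 = 0.455 or 0.50/0.659 = 0.759, and Arm B falls to 29.5% or 23.9%.
- **Reversal.** In the last row, Arm A has r = 0.95 × 0.88 = 0.836 and I(23) = 30.0%. That is below Arm B at f = 30% and above it at f = 50%.

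**What the added tables would show.** First events per patient-cycle at risk are I(K) divided by (1−r^K)/(1−r), which equals q. That is 0.050 in both arms, but only because the model assumes constant risk and a cut unrelated to risk. Twelve weeks is 84/21 = 4 cycles; with the cut after Cycle 5, both arms give 0.05 × (1−0.874^4)/0.126 = 16.5%.

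**The case against.** The strongest objection concerns direction. A reader might infer that the crude tables will make 4.7 mg/kg look safer than it is. The documents do not support that as a certainty, because they give no exposure by arm. Earlier stopping in Arm A can offset or reverse the effect, and early-onset toxicity shrinks it. This stands; but a reversal is also a product of observation time, so the need to show time at risk remains.

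A reader might also infer that the safety plan ignores time altogether. It does not. The by-cycle shift tables include platelets, neutrophils, hemoglobin, ALT, AST and bilirubin, which matters because the protocol names cytopenias as dose-limiting and liver abnormalities as the events of concern. Early mortality has fixed windows, and exposure is tabulated. Details of the hepatic tables are left to the Data Presentation Specifications, which are not among the documents. These outputs help, but none corrects an adverse-event percentage.

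Third, Protocol 11.1 evaluates the arms independently, SAP 2.3.8.1.1 plans no between-arm comparison (under efficacy), and Arm B was closed after the first interim review. So no test is biased, and that the arms' safety columns will be compared is an inference. The point is limited to how descriptive tables are read.

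Finally, a rate per patient-cycle is not free of bias. Censoring subjects selected for tolerance leaves less tolerant subjects at risk at 4.7 mg/kg. This stands and shapes the fix.

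**Conclusion.** The point holds as a limitation of the descriptive safety tables. Crude incidence, combined with a cut at escalation in one arm only, mixes toxicity with observation time. If exposure is otherwise equal, the percentages tend to understate toxicity at 4.7 mg/kg: by about 5 to 9 points in the base illustration and about 1 to 2 points with front-loaded risk, with a possible reversal if Arm A stops earlier. Those sizes rest wholly on the assumed hazard, discontinuation, cap, share escalated and timing; they are not estimates for this trial. The by-cycle laboratory tables, fixed-window mortality and exposure summaries mitigate the problem in part.

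**What to change.** Keep the crude tables. In SAP 2.3.9.1, for all treatment-emergent events, Grade 3 or higher events, serious events and hepatic events, add two supportive descriptive tables by arm:

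1. Incidence within the first 12 weeks, cut at escalation. This should lead, since it depends least on late truncation. It is fully common only where escalation came after Week 12, so the number cut earlier should be footnoted.
2. Subjects with a first event per 100 patient-cycles at risk, with time at risk ending at first event, escalation, or 30 days after last dose, whichever is earliest.

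State with the second table that it assumes a roughly constant hazard and non-informative censoring at escalation. Because escalators had laboratory values within the entry limits and no earlier dose reduction, the rate may overstate toxicity at 4.7 mg/kg and should be read with the 12-week table.

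The cost is a little programming from dosing and event dates already collected. No existing table is lost.
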